7.4 Supplemental Analyses of the Primary Outcome Measure

Adjusting for demographic and baseline characteristics in the analysis of randomized clinical trials is advised by both the European Medicines Agency [10] and the US Food and Drug Administration [11] in order to increase the precision of the estimator for the treatment effect, that is to increase statistical efficiency and avoid conditional bias from covariate imbalance. A mixed effects regression model using the ITT population will include more individual-level covariates which may be associated with the response. Those individual-level covariates pre-specified in the protocol were expected to have an influence on the primary outcome, including demographic variables, baseline measures of risk behaviors, substance use at baseline, presence of alcohol or drug use disorder, pain ratings, mental health symptoms or conditions, and health-related quality of life. Table 3 lists the covariates that will be used to explore the relationship of the treatment effect on the primary outcome adjusting for potential covariates.

Table 3: Potential individual-level covariate variables

Covariate	Source variable names¹	Coding in analysis	Description of covariate
Site	COREVARS.SITE	categorical	5 sites
Sex	COREVARS.SEX_CAT	categorical	Male/Female
Age	COREVARS.AGE	continuous	Age at enrollment
Ethnicity	COREVARS.ETHNIC	categorical	Hispanic/Non-Hispanic
Race	COREVARS.RACE_CAT	categorical	Black/White/Other
Education	DEM.DEEDUCTN	categorical	Less than Bachelor's degree/Bachelor's degree and above
Marital Status	DEM.DEMARTL	categorical	Married + Living with partner/Other
Job	DEM.DEJOB	categorical	Working now/Retired/Other
Baseline Risky Opioid use	COREVARS.OPI30 (HLS)	continuous	Number of days of risky opioid use during past 30 days prior to baseline assessment

Table 3: Potential individual-level covariate variables

Covariate	Source variable names¹	Coding in analysis	Description of covariate
Prescription Opioid Misuse Behaviors (COMM) at Baseline	COREVARS.CMMSCR (HLS)	continuous	Score to measure opioid misuse behaviors at baseline
Alcohol Use Disorder at Baseline	COREVARS.AUDSCR (PDQ)	continuous	Score to measure alcohol use disorder at baseline
Drug Use Disorder at Baseline	COREVARS.DUDSCR (PDQ)	continuous	Score to measure drug use disorder at baseline
Overdose risk behavior at Baseline	COREVARS.ORBSCR (ORB)	continuous	Score to measure overdose risk behavior at baseline
Pain severity at Baseline	COREVARS.BPISCR_SEV (BPI)	continuous	Score to measure pain severity at baseline
Pain interference at Baseline	COREVARS.BPISCR_INT (BPI)	continuous	Score to measure pain interference or functioning at baseline
Anxiety symptom at Baseline	COREVARS.PMASCR (PMA)	continuous	Score to measure anxiety symptoms at baseline
Depression Symptoms at Baseline	COREVARS.PHQSCR (PHQ)	continuous	Score to measure depression symptoms at baseline
Sleep quality at baseline	COREVARS.PMSSCR (PMS)	continuous	Score to measure sleep disturbance at baseline
Health-related Quality of Life at Baseline	COREVARS.SFMSCR (SFM)	continuous	Score to measure overall health-related quality of life at baseline

¹ Covariates that are calculated or scores are in the COREVARS analysis dataset and are derived from the data from the form name listed in parentheses.

The aim of covariate adjustment is not to determine the true relationship between covariates and the primary outcome variable but to provide an unbiased estimate of the true treatment effect. The regression model is based on a linear relationship between the covariates and the primary outcome when the covariate is continuous. However, increasing the number of covariates can decrease the power of the study and cause collinearity, so the following steps will be taken to identify the covariates to be included in the regression model:

1. Include the two covariates of site (stratification factor) and baseline value of response as identified in the primary outcome analysis model in Section 7.2.2.
2. Include all covariates from Table 3 that will result in 70% or more of the ITT population being included in the analysis. Since the mixed effect model will remove the entire patient record from the analysis if it is missing any covariate value, covariates with a significant amount of missing data will be removed.

3. Run correlation analyses among the covariates, and select the covariate set with low or moderate correlation to avoid collinearity and provide efficiency gains.
4. To gain analytical power, a general rule of thumb is that 10-20 observations should be used for estimating a parameter [12]. If the number of covariates after steps 2 and 3 is more than 10, the distributions of the remaining covariates will be compared by intervention group to select the potential confounders associated with baseline imbalances.

Multiple imputation will not be performed in the individual-level covariate adjusted regression model. The estimates of treatment effect will be compared between the regression models with and without the individual-level covariate adjustment to assess the robustness of the conclusion drawn from the primary analysis.

Subgroup analyses for sex (Male, Female), age (18 – 54 years, 55 years or greater), race (Black, White, Other) and ethnicity (Hispanic or Latinx, Not Hispanic or Latinx) will be performed as required by the NIH [13]. Responses of “Unknown,” “Don’t know” and “Refused to answer” will not be analyzed. These subgroup analyses will utilize the same mixed-effect model as for the primary outcome analysis, but with the inclusion of an interaction term between treatment arm and the demographic subgroup. Contrasts will be used to test for statistically significant differences in the primary outcome hypothesis by subgroup.

An analysis using the Per Protocol (PP) population will be performed using the same methods as described in Section 7.2.2. This population will exclude participants who had appointments with PCPs in the opposite treatment arm or had deviation from the protocol in terms of intervention exposure including the participants who were shown the wrong video doctor. No multiple imputation will be conducted for the PP population.

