In the example in Table 2, Group 1 consists of 160 patient participants who completed the risky opioid use questions in all 6 months, which covers 80% of the total 200 observations (160/200) with a mean of 24 days of risky opioid use in month 1 and a mean of 21 days of risky opioid use in month 2. Groups 2 and 3 present two monotonic missingness data patterns in which patient participants drop out after the Month 5 and Month 4 surveys, respectively. Groups 4 and 5 present two non-monotonic missing data patterns showing intermittent missingness.

The impact of missing data depends on the missingness mechanism, of which there are three: Missing Completely at Random (MCAR), Missing at Random (MAR) and Missing Not at Random

(MNAR). In MCAR, missingness is unrelated to any measured or unmeasured characteristic, and the missing observations are a random subset of all observations. In this study, MCAR is unlikely and is not considered further. In MAR, there may be systematic differences between the missing and observed values, but they can be explained by other observed variables and with MNAR, the missingness can only be explained by unobserved data.

Five missing data patterns for risky opioid use (no missing data, intermittent missing, missing due to dropout, both intermittent missing and missing due to dropout, and all missing) will be summarized by treatment arm in the ITT population. The number and percentage of patient participants with each individual pattern and a summary of number of patient participants per pattern will be presented by treatment arm.

For CTN-0101, the following assumptions will be made:

1. For the patient participants with intermittent missingness, assume MAR.
 - While the missingness are from intermittent missingness, in which an unobserved outcome can be followed by observed outcomes since the patient participants remain in the assigned intervention group, therefore the observed outcomes can effectively predict the propensity of the missing values and the missing mechanism is missing at random (MAR).
2. For the patient participants who dropout, assume MNAR.

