² Results for the treatment effect are obtained from the mixed effects negative binomial model adjusted for site (stratification factor) and baseline value of the response. Missing values of the variables that contribute to the primary outcome and baseline value of the response are not imputed.

³ The rate ratio is defined as the exponentiated estimate of the treatment effect as a ratio of the mean total number of days of risky opioid use for those enrolled to STOP versus EUC within the first 180 days post-baseline.

Table 34: Summary of Primary Outcome Analysis by Treatment Arm Using Multiple Imputation Assuming Missing at Random¹ in ITT Population

Treatment Arm	Number of Participants Enrolled	Days of Risky Opioid Use in the 180 Days from Baseline (Mean (SD))	Results ²			
			Rate Ratio ³	95% Lower Confidence Limit	95% Upper Confidence Limit	p-value
EUC	N	X.x (X.xx)	X.xx	X.xx	X.xx	0.xxx
STOP						
Total						

¹ Assuming a missing at random (MAR) for missingness due to both intermittent missingness and dropout is used for multiple imputation of the missing data in the sensitivity analysis.

² Results for the treatment effect are obtained from the mixed effects negative binomial model adjusted for site (stratification factor) and baseline value of the response. All of missing values from the variables of the primary outcome from Months 1-6 and baseline value of the response are imputed via multiple imputation assuming missing at random (MAR) for both intermittent missingness and for dropouts.

³ The rate ratio is defined as the exponentiated estimate of the treatment effect as a ratio of the mean total number of days of risky opioid use for those enrolled to STOP versus EUC within the first 180 days post-baseline.

10 Supplemental Analyses of Primary Outcome

Table 35: Summary of Primary Outcome Analysis with Individual-level Covariate Adjustment by Treatment Arm

Treatment Arm	Number of Participants Enrolled	Number of Participants Contributing to Analysis ¹	Days of Risky Opioid Use in the 180 Days from Baseline (Mean (SD))	Results ²			
				Rate Ratio ³	95% Lower Confidence Limit	95% Upper Confidence Limit	p-value
EUC	N	N (%)	X.x (X.xx)	X.xx	X.xx	X.xx	0.xxx
STOP							
Total							

¹ A participant contributed to the analysis if they have no missing values in the response variable and all of the covariates adjusted in the mixed effect regression model.

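### The covariate-adjusted check in SAP 7.4 is likely to pick covariates by between-arm imbalance, and it changes covariates, patients and missing-data assumption together, so it cannot cleanly isolate the effect of adjustment

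*SAP*

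**What the plan says.** SAP 7.4 says covariates are added "in order to increase the precision of the estimator for the treatment effect", and also to guard against bias conditional on imbalance. Protocol 14.6 left the choice of covariates to the SAP. The SAP starts from a named list (Table 3) and works in four steps.

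1. Site and baseline days of use are always kept.
2. A missingness filter: "Include all covariates from Table 3 that will result in 70% or more of the ITT population being included in the analysis".
3. A correlation filter, with no numerical cut-off.
4. "If the number of covariates after steps 2 and 3 is more than 10", then "the distributions of the remaining covariates will be compared by intervention group to select the potential confounders associated with baseline imbalances". No test, threshold or number to keep is given.

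On missing data the section states: "Multiple imputation will not be performed in the individual-level covariate adjusted regression model". Note 1 to the Table 35 shell (SAP 18.1) confirms a complete-record analysis: "A participant contributed to the analysis if they have no missing values in the response variable and all of the covariates adjusted". Note 2 leaves the covariate list blank. Estimates with and without adjustment are then compared "to assess the robustness of the conclusion drawn from the primary analysis".

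That primary analysis (SAP 7.2.3) uses 30 imputed datasets. Intermittent gaps are treated as missing at random. For the rest the rule is "For the patient participants who dropout, assume MNAR", implemented by control-based imputation.

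**The concern.** A covariate improves precision to the extent that it predicts the outcome. It causes conditional bias only if it is both imbalanced and predictive. Step 4 looks at imbalance alone, so it may keep an imbalanced covariate that predicts little and drop a strong predictor that happens to be balanced. With no stated criterion, the final model also depends on a judgement made after baseline data have been seen by arm.

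The second problem is the comparison. Going from the primary result to Table 35 changes three things: the covariates, the patients analysed, and the assumption about missing outcomes. If the estimates agree, offsetting changes cannot be excluded. If they differ, the cause is unknown. A published statement that the result was robust to covariate adjustment would lack a clear basis.

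Selective loss is plausible. Protocol 10.4 lets the mental health, sleep and quality-of-life forms be completed up to three weeks after the baseline visit. Protocol 11.11 does not count skipped or late forms as deviations. Patients without these scores may differ from the rest in engagement and in opioid use.

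**Working it through.** **How likely is step 4?**
- Table 3 has 19 covariates.
- COMM goes only to patients who report prescribed opioids (Protocol 11.4.4). Protocol 8.2.2 expects 15-20% of the sample to be receiving them, far below the 70% floor. That leaves 19 - 1 = 18, or 16 beyond site and baseline use.
- To avoid step 4, step 3 must remove at least 18 - 10 = 8, or 16 - 10 = 6 if site and baseline use are not counted. Step 4 is therefore likely, not certain.

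**Chance imbalance.** The SAP gives no criterion, so assume p < 0.05 and independent covariates. The probability that at least one is flagged by chance is 1 - 0.95^k.
- k = 16 (nothing removed in step 3): 0.56.
- k = 9 (11 left, including site and baseline use): 0.37.

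**What does the 70% floor mean?** The figure is a rule, so there is nothing to reproduce. Planned size is about 300 (SAP 2.1), and up to 20% may lack the primary outcome (SAP 7.2.3).
- Joint floor, outcome included: 0.70 x 300 = 210 kept, 30% lost.
- Floor on covariates only: 0.70 x 0.80 = 0.56, so 168 kept and 44% lost.
- Floor applied one covariate at a time: the joint loss has no cap.

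**Cost of the loss.** I simulated SAP section 10's Condition C (60 PCPs, 5 patients each): two binomial counts out of 90 days, with PCP and patient intercept variances 0.15 and 0.25 taken on the logit scale. A negative binomial model with random PCP intercepts was fitted to 1000 trials per scenario.
- Check on inputs: the middle 50% of control PCP means came to 17.2-25.3, against 17-25 in the SAP.
- Check on power, Scenarios 1 to 4: 0.966, 0.919, 0.982, 0.953 with all 300 analysed, against 0.97, 0.93, 0.99, 0.97 in the SAP. With 20% removed: 0.944, 0.891, 0.971, 0.935. The SAP's simulation code is not in the documents, so I draw no conclusion from that gap, and it does not bear on this point.

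Refitting the same Scenario 1 trials on random subsets:

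| Kept | SE of log rate ratio | Power |
|---|---|---|
| 100% (300) | 0.089 | 0.966 |
| 80% (240) | 0.093 | 0.944 |
| 70% (210) | 0.095 | 0.933 |
| 56% (168) | 0.101 | 0.905 |

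SE ratio, 70% against full: 0.095 / 0.089 = 1.07. Against the 80% subset: 0.095 / 0.093 = 1.02.

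At 70%, random loss alone shifts the rate ratio by a factor of up to 1.07 (95% range). It changes significance in 3.5% (Scenario 1) to 6.5% (Scenario 2) of trials. At 56% the factor is 1.10, and significance changes in 7.5% to 9.6%.

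**Does SAP 7.3 separate the causes?** Its complete-case fit (Table 33) needs the six monthly outcomes and baseline use. Table 35 needs those and every added covariate, so its patients are a subset. With 20% of outcomes missing and a joint 70% floor, the sets are 240 and 210. Going from one table to the other still adds covariates and drops 30 patients.

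**The case against.** The strongest reply is that the plan is more disciplined than it may look. A reader might infer that imbalance is the general selection rule. It is a conditional fourth step, within a pre-specified list of variables expected to influence the outcome, and it uses no outcome data. Imbalance is also relevant to the second stated aim. PCPs know their arm, and SAP 5.2 expects that patient-level balance may be poor because randomization is by PCP cluster. All of this stands. It narrows the criticism of step 4 but does not supply a threshold or weigh prognostic strength, and it does nothing for precision.

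A second reply is that SAP 7.3 already provides a non-imputed fit of the primary model and a repeat imputation under missing at random. Read in sequence, the primary result, Table 33 and Table 35 separate much of the change in missing-data handling from the adjustment. That also stands, but only in part. SAP 7.4 does not name Table 33 as the comparator, the patients may still differ, and the Table 35 shell has no place for an unadjusted fit on its own records.

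A third reply is that missing scores may be few. Protocol 10.4 says the post-visit forms are mostly done the same day or within a week. SAP 3.4 prorates scores when fewer than 20% of items are missing, and step 2 removes poorly completed covariates. The documents give no completion rates, so the extent of loss is open.

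**Conclusion.** The point holds in limited form. If step 4 applies, covariates are chosen by observed imbalance with no threshold and no regard to prognosis. Whether or not it applies, the comparison with the primary result mixes three changes and cannot cleanly attribute agreement or difference to adjustment.

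Three stronger readings are not supported:
- That the check has no value for robustness. SAP 7.3 separates part of the mixture, and random loss alone moves the estimate little.
- That keeping 70% of patients widens the standard error by 20%. That is 1/sqrt(0.70) = 1.195, which treats patients as independent. With the SAP's PCP variance the figure is about 7%.
- That the primary conclusion is at risk. This is a supplemental analysis; the primary model and its two-sided 5% test (SAP 9.0) are untouched.

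The 7% rests on the SAP's planning values, loss purely at random, and a full-data reference that the imputed primary will not quite reach. The simulation added no covariates, so the precision gain from adjustment is not quantified. More overdispersed or zero-inflated data, which SAP 14.1 anticipates, would give larger shifts. Selective loss could bias the adjusted estimate by an amount that cannot be sized from the documents.

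**What to change.** In SAP 7.4:

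1. Replace step 4 with a short list from Table 3, chosen on expected prognostic value and fixed without reference to arm. If baseline tables by arm have already been seen, record that with the list.
2. State that the 70% floor is joint across the covariates and counts missing outcomes.
3. Choose one comparison. Either refit the unadjusted primary model on exactly the records used for the adjusted model, report both in Table 35, and base the comparison on that pair. Or create a separate set of imputed datasets that includes these covariates and fit both models to it.

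The primary imputation should stay as it is; adding covariates to it would alter the primary analysis to serve a supplemental one.

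The cost is SAP wording and one or two extra model runs, plus a separate imputation under the second option. The first option is cheaper and settles attribution, but it leaves any bias from selective missingness in both fits.

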7.5 Definition of Other Outcome Measures Related to Primary Objective

Related to the primary objective, the hypothesis (H1.2) is that patient participants with primary care providers assigned to the STOP intervention will have fewer days of risky opioid use, measured at 3, 9, and 12 months from baseline, in comparison to patient participants with primary care providers assigned to EUC. The 3-month secondary outcome measure will assess early intervention effects, while the 9- and 12-month secondary outcome measures will assess the durability of intervention effects (which may be maintained, increased, or decreased) over time.

Therefore, the other outcomes related to the primary objective include days of risky opioid use at specified time points:

- i. In the past 30 days, measured at baseline and monthly for 12 months.
- ii. In the past 90 days, assessed at 3, 6, 9, and 12 months.
- iii. In the past 180 days, assessed at 12 months.

7.6 Supportive Analysis of Other Outcome Measures Related to Primary Objective

Data for the supportive analysis of other outcomes related to the primary objective will be from the HLM survey, and no imputation of missing outcome data will be conducted for those outcomes. The ITT Population will be used for the analyses.

Visualization presentation using box plots and descriptive summary statistics including mean, standard deviation, median and range will be provided for days of risky opioid use in the past 30 days measured at baseline and monthly for 12 months, in the past 90 days measured at 3, 6, 9, and 12 months, and in the past 180 days measured at 6 and 12 months by intervention treatment arm.

Treatment effect, time variability, and temporal trends will be evaluated for risky opioid use during the past 30 days based on a longitudinal data framework treating monthly risky opioid use as a count outcome. A mixed effects negative binomial model will be fit including treatment, time, and the interaction of treatment \times time to explore time trends and time variability between the two treatment arms through the 12 months of the study period. Time trend analysis will be repeated for monthly observations of the 30-day sum of risky opioid use days in order to further understand and describe temporal patterns. The piecewise linear function will be used to accommodate varying trends of change in opioid use during different period segments. This function will allow accurate description and easy interpretation of the non-linear trend over time associated with change of opioid use throughout the 12 months of intervention and follow-up duration. A piecewise linear mixed-effects model allows different linear functions of time (varying time slopes) corresponding to breaking points (knots) during the whole study period. To investigate the time trend and time variability in change of risky opioid use, different breaking points will be assessed in conjunction with graphical presentation, e.g., a spaghetti plot, to depict the growth trajectory patterns. The final breaking points to fit the piecewise linear function of time will be determined by the data structure and statistical criteria of good of fit, e.g., AIC or likelihood ratio test.

Fixed effects include treatment, piecewise linear function of time, interaction of treatment \times piecewise linear function of time, baseline risky opioid use and site. A random effect term for patient participants will be included to account for the correlation of repeated measures within the same patient participant and within-PCP correlation of participant responses. The autoregressive covariance structure will be used to take into account the correlation of the repeated measures of monthly risky opioid use. This structure specifies that observations that are more proximate to one another are more correlated than those that are more distant.

The following is an example of a model with piecewise linear functions at the breaking point of month 6 to allow the slopes that represent the change in the outcome over time to vary between Months 1-6 and Months 7-12.

The SAS code to create a linear spline variable to specify time spline “timespl” equal to “0” when time is from Months 1 to Month 6, or equal to “time – 6” when the time is greater than Month 6 is as follows.

```
DATA datmonthly;
  SET datmonthly;
  Chgpoint=6;
  If time <= Chgpoint then timespl=0;
  else if time >Chgpoint then timespl = time - 6;
RUN;
```

The model investigates whether there is treatment effect on change of monthly risky opioid use over 12 months. The estimates of time and piecewise linear time spline will provide information on the change of risky opioid use before and after Month 6. The interaction terms of treatment with time and time spline assess the difference in change of opioid use associated with the treatment effect during the two time segments. The “Estimate” statement is used to derive the following estimates and corresponding p-values:

1. Difference of time slopes in change of risky opioid use during Months 1-6 between the two treatment groups
2. Difference of time slopes in change of risky opioid use during Months 7-12 between the two treatment groups.

```
PROC GLIMMIX DATA=datmonthly METHOD=quad;
  CLASS PATID PCP time treat site;
  MODEL daysmonthly = treat time timespl treat*time treat*timespl site baseline / solution
  DIST=negbin LINK=log ddfm=bw;
  RANDOM intercept / SUBJECT= PCP;
  REPEATED / SUBJECT=PATID TYPE=AR(1);
  Estimate "Difference of change Months 1-6"
  time 0 timespl 0 treat*time 1 -1 treat*timespl 0 0/ CL ilink;
  Estimate "Difference of change Months 7-12"
  time 0 timespl 0 treat*time 1 -1 treat*timespl 1 -1/ CL ilink;
```

RUN:

where

“datmonthly” is the name of the dataset with one row for each month of risky opioid use for each patient participant in a long format,

“daysmonthly” is the name of the outcome, a continuous variable indicating monthly use of risky opioid use (days),

“treat” is a binary indicator variable coded as “1” for intervention arm STOP and “0” for control arm EUC,

“time” is a continuous variable indicating the number of the month when the opioid use is collected,

“timespl” is a continuous variable equal to 0 when time is in Months 1-6, or equal to time – 6 when the time is months 7-12;

“baseline” is a continuous variable indicating the number of days of risky opioid use during past 30 days prior to baseline assessment,

“site” is a categorical variable for the 5 participating sites,

“month” is a categorical variable for month during the study,

“PATID” is a character variable representing patient participant ID, and

“PCP” is a character variable representing PCP clusters.

Comparison of the time trend measured by time slopes in change of risky opioid use in treatment arm STOP compared to EUC during Months 1-6 and Months 7-12 separately will be reported as the estimated risk ratio along with a 95% confidence interval given the linear combination of estimated parameters shown in the Estimate statement.

Another supportive analyses will explore temporal patterns of number of days of risky opioid use during the past 3 months. The 3-month (days of use in the first 90 days post-baseline) and 6-month (days of use in days 91-180 post-baseline) outcome measures will assess early intervention effects. The measures at 9 and 12 months (days of use in days 181-270 post-baseline and in days 271-360 post-baseline, respectively) will assess the durability of intervention effects (which may be maintained, increased, or decreased) over time. These data analyses will utilize a longitudinal mixed effect negative binomial regression model treating quarterly risky opioid use during months 1-3, months 4-6, months 7-9 and months 10-12 as the dependent count variables. Fixed effects include treatment, time indicator in terms of duration of past 3 months, site and an interaction between treatment and time indicator. Time indicator will enter the model as a categorical variable (1 for months 1-3; 2 for months 4-6; 3 for months 7-9 and 4 for months 10-12) to allow greater flexibility. A random effect term for patient participants will be included to account for correlation of repeated measures on the same patient participant and within-PCP

correlation of participant responses. The template SAS code to fit the model in estimating treatment effect of STOP during Months 1-3 is given below.

```
PROC GLIMMIX DATA=datquar METHOD=quad;
  CLASS PATID PCP time treat site;
  MODEL daysquar = treat|time site baseline / solution DIST=negbin LINK=log ddfm=bw;
  RANDOM intercept / SUBJECT= PCP;
  REPEATED intercept/ SUBJECT=PATID TYPE=AR(1);
  Estimate "Treatment effect during Months 1-3" treat 1 -1 treat*time 1 0 0 0 -1 0 0 0/ CL
  ilnik;
  Contrast "Treatment effect during Months 1-3" treat 1 -1 treat*time 1 0 0 0 -1 0 0 0/ CL
  ilnik;
RUN;
```

where

“datquar” is the name of the dataset with one row for each quarterly risky opioid use for each patient participant,

“daysquar” is the name of the outcome, a continuous variable indicating quarterly use of risky opioid use (days),

“treat” is a binary indicator variable coded as “1” for intervention arm STOP and “0” for control arm EUC,

“time” is a categorical variable to indicate the time of past 3 months,

“baseline” is a continuous variable indicating the number of days of risky opioid use during past 30 days prior to baseline assessment,

“site” is a categorical variable for 5 participating sites,

“PATID” is a character variable representing patient participant ID, and

“PCP” is a character variable representing PCP clusters.

The treatment effect of STOP from this model will be presented as a rate ratio given the treatment effect and interaction of treatment x time along with a 95% confidence interval. The STOP intervention’s ability to reduce risky opioid use during months 1-3 compared to EUC is assessed by the treatment effect and interaction of treatment x time of the duration of months 1-3. The rate ratio, 95% confidence interval, and p-value will be reported for the treatment effect during months 1-3. Similarly, treatment effects of durations of months 4-6, months 7-9 and month 10-12 are obtained from the same mixed effect model.

To assess the number of days of risky opioid use during the past 180 days measured at 12 months, the data will be analyzed with a longitudinal mixed effect negative binomial regression model treating days of risky opioid use during months 1-6 and months 7-12 as the dependent count variable. The model for past 180 days is similar to the one for past 90 days specifying time indicator as a categorical variable (1 for months 1-6, and 2 for months 7-12). The STOP intervention’s ability to reduce risky opioid use during months 7-12 compared to EUC is assessed by the treatment effect and interaction of treatment x time of the duration of months 7-12.

